1. Presence of DVT on pre-operative screening ultrasound study.
2. Massive tumor (>20 cm in greatest dimension)
3. Amputation of the affected leg as treatment for tumor.
4. Estimated blood loss >2 liters during surgery.
5. Surgical drain output >500 cc of bloody fluid during first 8 hours.
6. I.N.R. >1.3 pre-operatively or > 1.5 post-operatively.
7. Platelet count < 100,000 either pre-operatively or post-operatively.
8. Indwelling post-operative epidural catheter for pain control.
9. Age <30 years.
10. History of underlying bleeding disorder, such as hemophilia.
11. History of adverse reaction to heparin such as heparin-induced thrombocytopenia.
12. Severe liver or renal insufficiency.
13. History of hypertensive or diabetic retinopathy.
14. History of gastro-intestinal bleeding within 12 months.
15. Treatment with warfarin, clopidogrel, aspirin, NSAIDs, LMWH or other anti-coagulants for conditions.
16. History of stroke.
17. Women of childbearing potential having a positive serum or urine pregnancy test (hCG) at the time of pre-operative evaluation (within 7 days of surgery).
18. Women who are breast feeding.
19. Hemoglobin < 8.0 gm/dl
20. Platelet count < 100,000 /L
21. Alanine aminotransferase >100 IU/L
22. Aspartate aminotransferase > 100 IU/L

23. Direct bilirubin >0.5 gm/dL (the laboratory does not perform direct bilirubin if total bilirubin is below 0.2 mg/dl since direct bilirubin cannot be greater than total bilirubin).
24. Serum creatinine > 2.0 gm/dL
25. Patients taking COX-2 inhibitors.
26. Patients who have fragmented mechanical heart valves.

Study Design

The study design will be an open-label, non-randomized clinical trial involving 25 – 35 consecutive patients in each of the two groups. Historical controls from this institution will be used to compare peri-operative bleeding events, drainage, transfusion requirements, and re-operation rates in similar patients who did not receive chemical prophylaxis for DVT. Published historical controls will be used to compare the DVT rate. The rate of DVT will be measured in this study, but the primary objective is to examine bleeding complications at the surgical site. The sample size therefore is not calculated to establish efficacy, which has been demonstrated for patients in general in numerous previous articles.

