The study design will be an open-label, non-randomized clinical trial involving 25 – 35 consecutive patients in each of the two groups. To analyze wound complications historical controls will be identified through the Surgical Database maintained by the Section of Orthopaedics from this institution and will be used to compare peri-operative bleeding events, drainage, transfusion requirements, and re-operation rates in similar patients who did not receive chemical prophylaxis for DVT. Data from surgery, including drain output, transfusion requirements, wound complications, and re-operation for wound problems will be collected. To analyze DVT rates and to compare against patients who did not receive, data from the previously published article by Lin et. al. will be used for the control group of patients with mechanical compression stockings alone. Patients will receive a combination of dalteparin, bilateral TED hose, and bilateral mechanical compression stockings while in the hospital.

Method of DVT Prophylaxis

Patients will receive a combination of dalteparin, bilateral TED hose, and bilateral mechanical compression stockings while in the hospital.

The reason for employing both mechanical prophylaxis and dalteparin together is as follows. DVT prophylaxis is very difficult to achieve. The DVT rate is never zero. There is a very little, if any, adverse effects of using mechanical compression stockings. However, from the previous study at Memorial Sloan-Kettering, it is known that there is still a significant rate of DVT (17%) with mechanical prophylaxis. Dalteparin and other low molecular weight heparins may improve upon this rate. There is no contraindication to using both dalteparin and mechanical prophylaxis together. The study is not intended to show that dalteparin obviates the need for mechanical prophylaxis.

Patients should not receive other anti-coagulants, such as aspirin, non-steroidal anti-inflammatory drugs, and warfarin while on the study. Heparin should not be administered except for routine intravenous catheter flushes.

During surgery, patients will have TED hose and a mechanical compression stocking on the unaffected extremity. For the operative leg TED hose and mechanical compression stocking will be applied in the recovery room.

Patients will be mobilized out of bed with physical therapy as soon as deemed safe by the attending physician (generally post-operative day 1).

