Patients will not continue dalteparin after discharge from the hospital. Patients are generally able to ambulate independently upon discharge, and are considered at reduced risk for DVT.

Dosing of Dalteparin

1. The unit dose will be 5000 units of dalteparin.
2. The dosing will be once a day.
3. The route of administration will be subcutaneous injection.
4. The medication will start 12 – 24 hours after surgery on post-operative day #1.
5. The medication will continue daily while the patient is in the hospital. A follow-up doppler ultrasound study will be obtained prior to discharge (post-operative day 5 – 14).

Screening for DVT

Each patient must have a pre-operative, bilateral doppler ultrasound study of the lower extremity veins, including the popliteal to the common femoral veins.

Patients will receive a post-operative bilateral doppler ultrasound study of the operative limb prior to discharge home (generally post-operative day 5 – 14).

The patients will be monitored by daily physical examinations while in the hospital. Signs of acute DVT include pain, tenderness to deep palpation, swelling and a positive Homan's sign. Both legs will be monitored by examination. Patients suspected of acute DVT will undergo emergent doppler ultrasound study. Signs of pulmonary embolus (PE) include shortness of breath, pleuritic chest pain, dyspnea, hypoxia, and an arterial-alveolar oxygen gradient. Patients suspected of acute PE will undergo emergent chest computed tomography and/or ventilation-perfusion lung scan.

Endpoints of Analysis

- 1) Post-operative blood loss, as measured by the number of units of packed red blood cells transfused after surgery and change in hemoglobin levels.
- 2) Post-operative drainage (cumulative) from surgical drains.
- 3) Re-operation rate for post-operative complications, including hematomas, seromas, and infections.
- 4) Rate of per-operative DVT in the study population.
- 5) Rate of post-operative DVT in the lower extremities.
- 6) Rate of clinically symptomatic pulmonary embolus.
- 7) Bleeding at distant sites, such as the gastro-intestinal tract.

Statistical Considerations

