Safety Monitoring. The primary endpoint for safety monitoring is the re-operation rate due to complications experienced by patients within the first 4 weeks after surgery. In the sarcoma group, surgery can be extensive and clinical experience indicates that approximately 10% of patients will require re-operation within 4 weeks.¹⁵⁻¹⁷ A 25% re-operation rate in this group of patients would be considered excessive. For the metastatic patient group, the surgery is typically less involved and the re-operation rate during the first 4 weeks is near zero.¹⁸ (we assume 3%) and a 15% re-operation rate would be considered excessive. We will monitor this endpoint separately for these two patient groups using the sequential probability ratio test (Goldman 1987).¹⁹ We assume a type 1 error rate of 5% for both treatment groups. Table 1 contains the stopping rules for each patient group. For example, in the metastatic group, if 2 patients in the first 8 treated require re-operations to amend primary surgical complications, the protocol will stop accrual in this group. Similar, if 4 of the first 8 patients in the sarcoma group require re-

operation, accrual in this patient group will stop. The probabilities of detecting excessive re-operation rates if the true rates are as high or higher than stated above using these two stopping rules are 6% and 72% for the metastatic and sarcoma patient groups, respectively.

Table 1. Stop trial for excessive re-operation rate if the number of re-operations at or larger than listed (No. Re-operations) are necessary in the number of patients treated.				
	Metastatic Patients			
No. Re-operations	2	3	4	
No. Patients	8	25	25	
	Sarcoma Patients			
No. Re-operations	4	5	6	7
No. Patients	8	16	26	30

Analysis Plan. Several additional safety and efficacy endpoints will be estimated. These include pre-operative DVT incidence, surgical drain output, the number of transfusions, post-operative DVT's and others. For continuous variables (e.g., surgical drainage, number of transfusions) data will be summarized using the mean (s.d.) and median (range). For categorical variables (e.g., DVTs, gender) data will be summarized in frequency tables. 95% confidence intervals will be estimated for all outcomes. For categorical outcomes, outcome estimates will be estimated with standard errors no larger than 9% and 10% for the sarcoma and metastatic patients, respectively.

Cost of Study

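### The drainage and transfusion comparison with historical controls is unadjusted as written, and nothing says the early-bleeding exclusions apply to the controls

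*Combined protocol and SAP*

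**What the plan says.** The Study Design section sets up the safety comparison: "Historical controls from this institution will be used to compare peri-operative bleeding events, drainage, transfusion requirements, and re-operation rates in similar patients" who had no chemical prophylaxis. Its second paragraph gives the source, in that "historical controls will be identified through the Surgical Database maintained by the Section of Orthopaedics from this institution", and adds that "Data from surgery, including drain output, transfusion requirements, wound complications, and re-operation for wound problems will be collected". Neither paragraph gives the number of controls, their calendar period, a definition of similarity, or a method of comparison.

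The exclusion criteria include several bleeding measures that are known only during or after the operation: "Estimated blood loss >2 liters during surgery" (item 4), "Surgical drain output >500 cc of bloody fluid during first 8 hours" (item 5), "I.N.R. >1.3 pre-operatively or > 1.5 post-operatively" (item 6), and a platelet limit before or after surgery (item 7). Tumor size is limited to under 20 cm, and in Group B it must also exceed 5 cm.

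Under Dosing of Dalteparin, "The medication will start 12 – 24 hours after surgery on post-operative day #1". Operative blood loss and 8-hour drain output therefore precede the drug.

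On analysis, Statistical Considerations says: "For continuous variables (e.g., surgical drainage, number of transfusions) data will be summarized using the mean (s.d.) and median (range". It adds frequency tables for categorical variables and 95% confidence intervals for all outcomes. No between-group contrast is defined. Endpoint 2 is cumulative drainage, with no stated start time.

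**The concern.** The study's stated purpose is to learn whether dalteparin increases bleeding at the surgical site. There is no concurrent control, so any comparative statement about drainage or transfusion rests on the historical patients. The introduction itself says that bleeding risk varies considerably with the patient and the operation. A difference in operation size between study patients and controls can therefore look like a drug effect, or hide one.

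There are two separate routes to bias. First, if exclusions 4 to 7 are applied only to study patients, the study side is trimmed of its heaviest early bleeders and the control side is not. Second, even when both sides meet the same limits, they can differ within them: up to 2 L of blood loss, up to 500 cc of early drainage, and 5 to 20 cm of tumor in the sarcoma cohort. Measures that could reduce both problems must be known for study patients before the first dose, yet the plan uses them only as cut-offs.

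**Working it through.** **The plan's own precision figure.** The largest standard error of a proportion is √(0.25/n). For n = 30 it is √(0.25/30) = 9.1%; for n = 25 it is √(0.25/25) = 10.0%. These agree with the stated 9% and 10% after rounding. They describe precision within one cohort. No precision, SD or sample size is given for the comparison with controls.

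**Inputs.** Cohort sizes n = 30 (sarcoma) and n = 25 (metastatic) are from Statistical Considerations. Three inputs are assumptions, because the documents do not give them: the number of controls m (taken equal to n unless stated), the correlation ρ between a pre-drug bleeding measure and the later outcome (0.3 to 0.7), and the standardized imbalance D in that measure between groups (0 to 1.0 SD).

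**Formulas, in outcome SD units.**
- Crude SE = √(1/n + 1/m).
- Adjusted SE = √[(1 − ρ²)(1/n + 1/m + D²/(n + m − 2))].
- Size of the bias in the crude difference = ρ × D.

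**Bias.** At D = 0.5 and ρ = 0.3, 0.5, 0.7 the bias is 0.15, 0.25, 0.35 SD. The crude SE is 0.258 (n = m = 30) or 0.283 (n = m = 25). The difference detectable with 80% power at two-sided 5% is therefore about 2.80 × 0.258 = 0.72 SD or 2.80 × 0.283 = 0.79 SD, so the largest of these biases is nearly half of it. With no drug effect, a two-sided 5% test on the crude difference would reject this often:

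| Bias (SD) | n = m = 30 | n = m = 25 |
|---|---|---|
| 0.15 | 8.9% | 8.3% |
| 0.25 | 16.2% | 14.3% |
| 0.35 | 27.3% | 23.6% |

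If the controls bled more before the drug window, a true increase of 0.5 SD would appear as 0.5 − 0.35 = 0.15 SD to 0.5 − 0.15 = 0.35 SD. If the study patients bled more, the error runs the other way.

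**One-sided exclusion.** Assume lognormal blood loss with median 0.6 to 1.5 L and log-SD 0.6 to 0.8. Applying the 2 L limit to study patients only then shifts their mean blood loss by about 0.1 to 0.5 SD relative to unscreened controls. Multiplied by ρ, this is 0.3 × 0.1 = 0.03 SD to 0.7 × 0.5 = 0.35 SD in favor of dalteparin, from that single criterion.

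**Precision.** Ratio of adjusted to crude SE, n = m = 30:

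| ρ | D = 0 | D = 0.5 | D = 1.0 |
|---|---|---|---|
| 0.3 | 0.95 | 0.98 | 1.07 |
| 0.5 | 0.87 | 0.89 | 0.97 |
| 0.7 | 0.71 | 0.74 | 0.80 |

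At D = 0.5 the SE falls by 2% to 26%. At ρ = 0.3 and D = 1.0 it rises by 7%. With three or five controls per patient that last ratio is 1.04 or 1.02. These figures are for a single covariate; each further term costs a little more.

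**Re-operation.** At the plan's assumed base rates, the expected events are 30 × 0.10 = 3.0 and 25 × 0.03 = 0.75. That is too few to support covariate adjustment.

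**The case against.** The strongest reply is that the plan does not prescribe a crude analysis. A reader might infer that it does from the sentence on means and medians, but that sentence covers summaries of additional endpoints and does not mention controls, and the controls are at least described as similar. This stands: the defect is silence on method, which leaves an unadjusted contrast by default and leaves any other choice to be made after the data are seen.

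It is also fair that this is a preliminary study whose only decision rule is 4-week re-operation against fixed rates. No stopping decision depends on drainage or transfusion. That limits the weight of the point but does not remove it, because the Study Design section still commits to the comparison.

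Third, eligibility screening guarantees these measures for study patients only. The data-collection sentence does not name blood loss or tumor size, although its list is not exhaustive, and timed drain records for controls are not mentioned. Adjustment is possible only as far as the records allow.

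Fourth, the metastatic cohort is expected to have little drainage, so zeros are plausible and a log-drainage model may fail. With 25 patients, a model with several terms plus type of procedure would be too large. Both limits carry over to the fix.

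Finally, the eligibility limits narrow the range of the covariates, which tends to lower their correlation with outcome. That is why the working extends down to ρ = 0.3.

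**Conclusion.** The point holds as a bias-reduction measure for the continuous bleeding outcomes. The documents neither define the control group closely enough nor state how it will be compared, and pre-dose measures that would reduce confounding are not put to that use. Under the stated assumptions (ρ of 0.3 to 0.7, imbalance of 0.5 SD), adjustment would remove 0.15 to 0.35 SD of bias.

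Two stronger readings are tempting and not supported. One is that adjustment reliably narrows the interval: a reduction of 13% to 29% needs both a correlation of 0.5 to 0.7 and no imbalance, and the documents support neither. The other is that the bias must favor dalteparin. It does so if exclusions 4 to 7 are left off the controls, on which the documents are silent; otherwise its direction depends on which group bled more. The change should be made before control data are extracted, but the stopping rules do not depend on it.

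**What to change.** 1. Define the control group: calendar period, procedures and source records. Apply to it, wherever records allow, the same tumor-size, blood-loss, first-8-hour drain-output, INR and platelet exclusions. Report how many controls could not be screened on each.
2. For drainage and red-cell units, report beside the crude difference a pre-specified adjusted difference with its 95% CI. Keep the covariates few and measured before the first dose: operative blood loss, plus tumor size in the sarcoma cohort, plus first-8-hour drain output if it can be retrieved for controls.
3. Endpoint 2 has no start time, so it can contain the first-8-hour output. When that output is a covariate, count outcome drainage only after the 8-hour window in both groups, and keep total cumulative drainage as the stated endpoint.
4. In the metastatic cohort, use a model that allows zero drainage. Do not model re-operation; report it as counts with intervals.
5. State that adjustment addresses measured differences only.

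The cost is analysis wording, chart extraction for controls and a few degrees of freedom. No patient is added. If timed drain records are missing for controls, 8-hour output drops out as a covariate and cumulative drainage is adjusted for the remaining measures. If blood loss is missing too, the limitation should be reported with the crude comparison. Differences between eras and surgeons remain.

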Purpose:

1. The primary endpoint of the study would be to determine the safety of dalteparin as prophylaxis against deep venous thrombosis (DVT) in orthopaedic oncology patients. Specifically, the goal of the study is to determine whether there are significantly increased bleeding complications at the surgical site after major oncologic operations in the lower extremity.
 - a. The study would help establish specific parameters for use of dalteparin in complex orthopaedic oncology patients. Not all patients would be appropriate for this medication, particularly those with massive hemorrhage during surgery and those with underlying coagulopathies.
 - b. It is likely that patients requiring limited tumor excision, particularly those with metastatic carcinoma, would be ideal candidates for dalteparin therapy.
 - c. Patients who require radical resections of tumor may need stricter guidelines for the safe use of the medication, since the potential for post-operative bleeding may be greater.

Hypotheses:

1. Dalteparin may be used safely in complex group of patients such as orthopaedic oncology patients, provided that strict guidelines are followed with regard to indications for therapy.
2. Patients with metastatic carcinoma affecting the osseous skeleton would be good candidates for treatment since they generally have limited surgical resections and a pre-disposition to formation of DVTs.
3. The use of dalteparin would result in a low rate of DVTs that would compare favorably against historical controls.

Introduction:

It is well recognized that patients undergoing orthopaedic procedures such as total knee replacements and total hip replacements, are at increased risk of venous thromboembolic events.^{1,2} It is also known that cancer patients are at increased risk of venous thrombosis.³⁻⁵ There have been little written about venous thrombosis in cancer patients undergoing major resections and orthopaedic procedures in the lower extremities. It is not well documented in the literature what the prevalence and extent of the problem is.

The largest previous study was performed at Memorial Sloan-Kettering Cancer Center. This study focused on the role of mechanical compression boots in orthopaedic oncology patients.⁶ As expected, there is a high rate of proximal DVT's in the thigh even with mechanical prophylaxis (17%). This study did not address the potential use of low molecular weight heparins or other forms of anti-coagulation. Preliminary results from a

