The hypothesis is that the drug is safe for the patient population identified in this study. Most of the published safety data on the drug pertains to general orthopaedic patients and not to orthopaedic oncology patients. This study is intended to provide preliminary data on benefits and risks for orthopaedic oncology patients.

Orthopaedic oncology encompasses a wide array of patients. Some patients are healthy and normal except for their tumor. Other patients may be moribund with multiple co-morbidities. Some patients require a relatively small procedure to remove the tumor, while others require massive resections and reconstructions. The risk of post-operative bleeding complications for these patients would be expected to vary considerably.

As the first step toward establishing the use of dalteparin in orthopaedic oncology patients, it is proposed that two target populations be studied. One group of patients is

comprised of those with metastatic disease in the lower extremity. The other group of patients is composed of those who require major resection of sarcomas of the lower extremity.

The two groups of patients are inherently different. The patients with metastatic disease of the lower extremity are an important group since they encompass a large population of patients. These patients are believed to be at the highest risk for DVT. They tend to be older, more sedentary, less mobile, and have multiple comorbid conditions. These patients may be ideal candidates for treatments with dalteparin. The patients typically undergo a limited excision or curettage followed by an intramedullary rod, plating, cementation, hip arthroplasty or knee arthroplasty. The patients typically do not have much post-operative bleeding or drainage, since the skeletal defect is filled with bone cement. There is typically no significant dead space after surgery in which a large hematoma or seroma could form.

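### The DVT comparison sets two cohorts of different stated risk against one published series with a single quoted rate, and plans no tumor-group matching or allowance for the control's sampling error

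*Combined protocol and SAP*

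**What the plan says.** - **Hypotheses, item 3:** "The use of dalteparin would result in a low rate of DVTs that would compare favorably against historical controls". It names no cohort and sets no margin.
- **Study Design:** "Published historical controls will be used to compare the DVT rate". The same section then names one published series, whose data "will be used for the control group of patients with mechanical compression stockings alone".
- **Control rate:** 17% is the only figure quoted from that series. The Introduction gives it as a rate of proximal DVT. Method of DVT Prophylaxis repeats it ("it is known that there is still a significant rate of DVT (17%) with mechanical prophylaxis") and adds: "Dalteparin and other low molecular weight heparins may improve upon this rate".
- **Cohorts (Introduction):** "The two groups of patients are inherently different". Of the metastatic patients it says: "These patients are believed to be at the highest risk for DVT". No DVT rate is given for either cohort.
- **Statistical Considerations:** the two groups are evaluated as independent cohorts, 25 metastatic and 30 sarcoma patients. The Analysis Plan gives 95% confidence intervals for all outcomes, with standard errors for categorical outcomes of at most 9% (sarcoma) and 10% (metastatic).
- **Other controls (Study Design):** the institutional controls for bleeding, drainage, transfusion and re-operation are limited to similar patients. No such limit is placed on the DVT control.

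**The concern.** A single external rate is a fair comparator for a cohort only if the patients behind it carry about the same untreated risk. The protocol itself believes that the metastatic patients carry more. A published series that mixes diagnoses would then sit above the untreated sarcoma rate and below the untreated metastatic rate, so the comparison starts off biased in opposite directions in the two cohorts.

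The authors saw the need for separate benchmarks elsewhere: Safety Monitoring assumes re-operation rates of 10% in sarcoma and 3% in metastatic patients. Nothing equivalent is set for DVT. The planned intervals cover the trial's own rates, but nothing covers the uncertainty in the published rate.

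At stake is the reading of Hypothesis 3, and what the trial passes on to the larger studies it is meant to inform. A drug with no effect could seem to work in sarcoma and to fail in metastatic disease, the group that Hypothesis 2 regards as good candidates.

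**Working it through.** **Inputs from the documents:** n = 30 sarcoma and n = 25 metastatic (Statistical Considerations); quoted control rate 17% (Introduction; Method of DVT Prophylaxis).

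**Inputs assumed:** the untreated rate in each tumor group. The documents give neither these rates nor the case mix of the published series. I take sarcoma/metastatic pairs that average 17% in an equal mix: 14%/20%, 12%/22% and 10%/24%, with 17%/17% as the equal-risk reference.

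**1. The plan's own precision figure.** The largest standard error of a proportion is √(0.5 × 0.5/n). At n = 30 this is 9.1% and at n = 25 it is 10.0%, which matches the stated 9% and 10%. Both figures describe the trial's rates only. The standard error of a difference is √[p₁(1 − p₁)/n₁ + p₀(1 − p₀)/n₀]. The plan does not supply the second term, and the size n₀ of the published series is not quoted.

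**2. Point estimates with no drug effect.** A sarcoma estimate is below 17% at 5/30 (16.7%) or fewer. A metastatic estimate is above 17% at 5/25 (20%) or more. With X binomial and the cohorts independent, the joint probability is the product P(X ≤ 5; 30, p_S) × P(X ≥ 5; 25, p_M).

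| Untreated sarcoma/metastatic | Sarcoma below 17% | Metastatic above 17% | Both |
|---|---|---|---|
| 17%/17% | 59.7% | 42.4% | 25% |
| 14%/20% | 76.4% | 57.9% | 44% |
| 12%/22% | 85.7% | 67.2% | 58% |
| 10%/24% | 92.7% | 75.2% | 70% |

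**3. Sensitivity to the assumed mix.** Let w be the metastatic share of the published series and RR the metastatic-to-sarcoma risk ratio. Then p_S = 0.17/(w·RR + 1 − w) and p_M = RR·p_S.
- At w = 0.5, RR of 1.5, 2 and 3 gives sarcoma/metastatic rates of 13.6%/20.4%, 11.3%/22.7% and 8.5%/25.5%. The joint pattern occurs 47%, 62% and 77% of the time.
- At RR = 2 with w from 0.3 to 0.7, it occurs 54% to 67% of the time.
- If the risk ran the other way (RR = 0.5, w = 0.5), it would occur only 4% of the time. The result depends on the direction that the protocol states.

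**4. The planned 95% intervals (exact, Clopper-Pearson).** The sarcoma interval lies wholly below 17% only at 0/30, since 1/30 already has an upper limit of 17.2%. The probability is (1 − p_S)³⁰: 0.86³⁰ = 1.1%, 0.88³⁰ = 2.2%, 0.90³⁰ = 4.2%. The metastatic interval lies wholly above 17% only at 9/25 or more (lower limit 18.0% at 9/25). The probability is 4.7% at a true rate of 20%, 7.9% at 22% and 12.3% at 24%. With equal risk the two probabilities are 0.4% and 1.8%.

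**The case against.** A reader might infer that the plan tests each cohort against a pooled 17%. It does not say so. It refers to data from the article, which leaves room for subgroup counts. The 17% appears as background and as the rationale for combined prophylaxis, never as a criterion, and no success rule is set. The statement that the groups differ inherently is also general; only the sentence on highest risk concerns DVT, and it gives no numbers. What remains is a gap: subgroup use is not excluded, but neither is it planned.

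A reader might also infer that sampling error is ignored altogether. The Analysis Plan contradicts that for the trial's own DVT rate. Only the control's sampling error is left out.

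The percentages for point estimates rest on assumed rates and on reading an estimate below 17% as favorable, a rule the plan does not state. Chance alone puts a sarcoma estimate below 17% in 60% of trials. Read through the planned intervals, the effect is much smaller; 5/30 has an interval of about 6% to 35%, which plainly shows no benefit. This stands and limits the consequence. But the plan does not tie a favorable comparison to an interval, so a point estimate could carry the claim.

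The metastatic direction is not assured either. Both cohorts exclude patients with DVT on pre-operative screening, which could lower both observed rates if the published series did not do the same. The documents do not say whether it did.

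Finally, DVT is secondary, the sample size is expressly not set for efficacy, and the stop rule uses re-operation only. This argues for a modest change, with no confirmatory test added.

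**Conclusion.** The concern holds as a gap in specification. The plan compares DVT rates with one published series, believes that one of its own cohorts carries the highest risk, and specifies neither a tumor-group comparator nor an allowance for the control's uncertainty. If risk differs in the stated direction, the pattern of sarcoma favorable and metastatic unfavorable would appear with no drug effect in 44% to 70% of trials, against 25% with equal risk. That range rests on untreated rates of 14%/20% to 10%/24%, an equal case mix in the published series and a reading by point estimate.

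The documents do not support the stronger conclusion that the planned analysis would often produce a statistically persuasive false result. Under the same rates, the sarcoma interval would fall wholly below 17% in 1% to 4% of trials, and the metastatic interval wholly above it in 5% to 12%. The comparison should be repaired before it is reported, but accrual, treatment and stopping do not depend on it.

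**What to change.** In the DVT comparison under Study Design, with matching text in the Analysis Plan:

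1. Compare each cohort with the matching diagnosis stratum of the published series and, where the article allows, with the matching lower-extremity operation.
2. Report each difference with a two-sample 95% confidence interval that includes the control's sampling error. No significance threshold is needed, given that the trial is not sized for efficacy.
3. If stratum counts are not published but the case mix is, standardise the trial rates to that mix, as w × metastatic rate + (1 − w) × sarcoma rate, and compare only that single figure.
4. If neither is published, label the comparison descriptive and draw no favorable conclusion for either cohort.
5. State whether the published series excluded pre-operative DVT, as this trial does, or that this is unknown.

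The cost is a little data extraction from one cited article and a few sentences of plan text. Stratum-specific intervals will be wider. Eligibility, sample size and treatment are unaffected.
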